8.3.2 Direct access to source data and documents

The Investigator / institution will permit trial-related monitoring, audits, IRB review and regulatory inspection, providing direct access to all related source data / documents. eCRF and all source documents, including progress notes and copies of laboratory and medical test results must be available at all times for review by the Sponsor's clinical monitor, auditor and inspection by health authorities (e.g. FDA). The CRA and auditor may review all eCRFs, and written informed consents. The accuracy of the data will be verified by reviewing the documents described in [Section 8.3.1](#).

An adaptive approach to clinical trial monitoring will be utilised. This is initiated by an assessment of the risk associated with the trial combined with identification of critical data

and process. An Integrated Quality and Risk Management Plan documents the strategies involved with the implementation of onsite, offsite and central monitoring activities in order to direct focus to the areas of greatest risk which have the most potential impact to subject safety and data quality. Trial oversight is achieved by regular review of a report of risk which then influences any monitoring adaptations.

8.3.3 Storage period of records

Trial sites:

The trial sites must retain the source documents and essential documents for a period defined by the Japanese GCP regulation and trial site's contract with the sponsor.

Sponsor:

The Sponsor must retain the essential documents according to the Sponsor's SOPs.

8.4 LISTEDNESS AND EXPEDITED REPORTING OF ADVERSE EVENTS

8.4.1 Listedness

To fulfil the regulatory requirements for expedited safety reporting, the Sponsor evaluates whether a particular adverse event is "listed", i.e., is a known side effect of the drug or not. Therefore, a unique reference document for the evaluation of listedness needs to be provided. For empagliflozin this is the current version of IB [[c01838761](#)]. In addition to that the Japanese package insert of empagliflozin is used to assess local expectedness in Japan.

The current versions of these reference documents are provided in the ISF. No AE are classified as listed for matching placebo, trial design.

8.4.2 Expedited reporting to health authorities and IEC / IRB

Expedited reporting of serious adverse events, e.g. suspected unexpected serious adverse reactions (SUSAR) to health authorities and IRBs, will be done according to local regulatory requirements. Further details regarding this reporting procedure are provided in the ISF.

8.6 END OF TRIAL

The end of the trial is defined as the last patient out.

When the trial is completed, the Investigator should inform the head of the trial site of the completion in writing, and the head of the trial site should promptly inform the IRB and Sponsor of the completion in writing.

8.7 PROTOCOL VIOLATIONS

The investigator should document any deviation from the protocol regardless of their reasons.

Only when the protocol was not followed in order to avoid an immediate hazard to trial subjects or for other medically compelling reason, the principal investigator should prepare and submit the records explaining the reasons thereof to the sponsor, and retain a copy of the records.

8.8 COMPENSATION AVAILABLE TO THE PATIENT IN THE EVENT OF TRIAL RELATED INJURY

In the event of health injury associated with this trial, the Sponsor is responsible for compensation based on the contract signed by the trial site.

11. DESCRIPTION OF GLOBAL AMENDMENT(S)

Number of global amendment	1
Date of CTP revision	13 September 2016
EudraCT number	
BI Trial number	1245.107
BI Investigational Product	Jardiance [®] , Empagliflozin
Title of protocol	A 52-week randomised, double-blind, placebo-controlled, parallel-group, efficacy and safety study of empagliflozin once daily, as add-on to insulin in Japanese patients with Type 2 Diabetes Mellitus with insufficient glycaemic control
To be implemented only after approval of the IRB	
To be implemented immediately in order to eliminate hazard – IRB to be notified of change with request for approval	
Can be implemented without IRB approval as changes involve logistical or administrative aspects only	
Section to be changed	3.3.2 and synopsis (Change 1)
Description of change	Text in inclusion criteria 2 is reformulated to: Insulin product and its usage must be unchanged at least from 12 weeks prior to Visit 1 (screening). Total prescribed dose must be ≥ 10 U/day and ≥ 0.2 U/kg/day , and it has to be within a defined area at least 12 weeks prior to Visit 5 (randomization) in patients who are pre-treated by insulin alone and from Visit 1 in patients who are pre-treated by insulin in combination with 1 OAD.
Rationale for change	To carry out the study in common clinical setting in Japan, the criterion of the dose of insulin is updated. (It is estimated that there are many T2DM patients who are treated with insulin which doses are more than or equal to 10U/day but below 0.2U/kg/day in common clinical setting in Japan)
Section to be changed	3.3.2 and synopsis (Chang 2)
Description of change	Inclusion criteria 3 is reformulated to: Fasting C-peptide: $\geq 0.6 > 0.5$ ng/mL at Visit 4 in patients who are pre-treated with insulin alone (at

Proprietary confidential information © 2016 Boehringer Ingelheim International GmbH or one or more of its affiliated companies

		Visit 2 in patients who are pre-treated with insulin in combination with 1 OAD)
Rationale for change		The criterion was set up to remove the patients who are in insulin-dependent state. The treatment Guide for Diabetes 2014-2015 says that C-peptide ≤ 0.5 is insulin-dependent state. To match with the treatment guide, this is updated.
Section to be changed		5.3.6.1 (Chang 3)

## **2. LIST OF ABBREVIATIONS**

Term	Definition / description
AE	Adverse event
AESI	Adverse event of special interest
ALQ	Above Limit of Quantification
ALT	Alanine transaminase
ANCOVA	Analysis of covariance
AST	Aspartate transaminase
ATC	Anatomical-Therapeutic-Chemical classification
BC	Body composition (set)
BI	Boehringer Ingelheim
BICMQ	BI-customized MedDRA query
BLQ	Below the limit of quantification
BMI	Body mass index
BRPM	Blinded report planning meeting
CEC	Clinical event committee
CRF	Case report form
CT	Concomitant therapy
CTP	Clinical Trial Protocol
CTR	Clinical Trial Report
DBL	Database Lock
DBP	Diastolic blood prpressure
DI	Disposition index
DM&SM	Boehringer Ingelheim Data Management and Statistics Manual
eCcr	Estimated creatinine clearance rate
ECG	Electrocardiogram
eCCr	Estimated creatinine clearance
eCRF	Electronic Case Report Form
eGFR	Estimated glomerular filtration rate
EMA	European medicines agency
EoT	End of treatment
FAS	Full analysis set

Term	Definition / description
FPI	Fasting plasma insulin
gCV	Geometric coefficient of variation
gMean	Geometric mean
HbA 1c	Glycated haemoglobin
HCRU	Health care resource utilisation
HOMA-IR	Homeostatic model assessment - insulin resistance
HOMA-IS	Homeostatic model assessment - insulin secretion
ICH	International Conference on Harmonisation
INN	International non-proprietary names
IPV	Important protocol violation
IRC	Independent Review Committee
ITT	Intention to treat
IVRS	Interactive Voice Randomisation System
IWRS	Interactive Web Randomisation System
LOCF	Last observation carried forward
LQ	Limit of quantification
MDRD	Modification of diet in renal disease
MedDRA	Medical Dictionary for Regulatory Activities
MMRM	Mixed-effect Model Repeated Measures
MQRM	Medical Quality Review Meeting
NCF	Non-completers considered failure
O*C	Oracle Clinical
OC	Observed case
OC-IR	Observed cases, including values after rescue
OLS	Open label set
OR	Original results
PK	Pharmacokinetics
PPG	Postprandial glucose
PPS	Per protocol set

Term	Definition / description
PT	Preferred term
PV	Protocol violation
Q1	Lower quartile
Q3	Upper quartile
RS	Randomised set
SBP	Systolic blood pressure
SCR	Screened set
SD	Standard deviation
SDL	Subject data listing
SMQ	Standardised MedDRA query
SOC	System Organ Class
SSC	Special search category
SUB	Sub-searches
TBL	Total bilirubin
TOC	Table of contents
TS	Treated set
TSAP	Trial statistical analysis plan
ULN	Upper limit of normal
UTI	Urinary tract infection
WHO	World Health Organisation

### **3. INTRODUCTION**

As per International Conference on Harmonisation (ICH) E9, the purpose of this document is to provide a more technical and detailed elaboration of the principal features of the analysis described in the protocol, and to include detailed procedures for executing the statistical analysis of the primary and secondary variables and other data.

This Trial statistical analysis plan (TSAP) assumes familiarity with the Clinical Trial Protocol (CTP), including Protocol Amendments. In particular, the TSAP is based on the planned analysis specification as written in CTP Section 7 “Statistical Methods and Determination of Sample Size”. Therefore, TSAP readers may consult the CTP for more background information on the study, e.g., on study objectives, study design and population, treatments, definition of measurements and variables, planning of sample size, randomisation.

SAS® Version 9.2 or later version will be used for all analyses.

## **4. CHANGES IN THE PLANNED ANALYSIS OF THE STUDY**

All analyses described in this TSAP have already been outlined in the CTP. There are no changes compared to the planned analysis of the study.

## **5. ENDPOINTS**

### **5.1 PRIMARY ENDPOINT**

The primary endpoint in this study is the change from baseline in HbA1c after 16 weeks of treatment. Throughout the study protocol, the term "baseline" refers to the last observation prior to the administration of any randomised study medication.

### **5.2 SECONDARY ENDPOINT**

The secondary endpoint is proportion of patients with drug-related adverse events during 52 weeks of treatment.

## **6. GENERAL ANALYSIS DEFINITIONS**

### **6.1 TREATMENTS**

There will be four treatment phases in this trial: screening, study treatment phase (with 10 mg or 25 mg empagliflozin or matching placebo), post-treatment and post-study.

The purpose of the definitions below is to describe all the different study/treatment intervals, in which a patient can lie during the course of the trial. Note that the term "treatment regimen" can also cover time periods with no active treatment.

Table 6.1: 1 Treatment regimens / study intervals

Label	Interval	Start date	Start time
Screening	Screening	Date of informed consent	00:00
Placebo/ Empagliflozin 10mg/ Empagliflozin 25mg	Treatment	Date of first administration of study medication	Time of first administration of study medication 12:00 if missing
Post-treatment	Post-treatment	Date of last intake of study drug +1 day	00:00
Post-study	Post-study	Date of trial completion (in termination page of eCRF) + 1 day	00:00

For efficacy and safety analyses, measurements will still be considered on-treatment during a follow-up period specific to each parameter. These follow-up periods are defined in [Table 6.7: 1](#).

The efficacy analyses will follow the intention-to-treat (ITT) principle in assigning patients to treatment groups, i.e. patients will be analysed as randomised.

Safety analyses will assign patients to the treatment group as treated. If a patient erroneously receives the wrong trial drug, the patient will be analysed as per the first treatment received. The only exception will be drug-related adverse events (AE) which will be analysed based on the actual treatment taken at the time of the AE onset. Additionally, the AEs with an onset during the time of the incorrect study treatment will also be listed separately.

## **6.2      IMPORTANT PROTOCOL VIOLATIONS**

Not all important protocol violations (IPV) will generate exclusion from the per protocol population. Violations that lead to exclusion from analysis populations are indicated as such in [Table 6.2.1](#)

The decision about which IPV could generate exclusion from analysis sets will be taken during the course of the study and finalised at the last blinded report planning meeting (BRPM).

Table 6.2: 1 Important Protocol Violations

Category / Code	Description		Comment/Example	Excluded from
A	Entrance Criteria Not Met			
A1	Target indication not met			
	A1.01	No type 2 diabetes	INC1 checked	PPS
	A1.02	Antidiabetic background therapy not as required	INC2 checked	PPS
A2	Inclusion criteria violated			
	A2.01	HbA 1c out of range	HbA 1c out of range for inclusion by more than 0.2% for insulin alone: [7.5%, 10%] at Visit 1 for insulin with 1 OAD: [7.0%, 9.5%] at Visit 1 [7.5%, 10%] at Visit 4	PPS
	A2.02	Age out of range	INC6 checked and calculated date checked	None
	A2.03	BMI out of range	INC7 checked	None
	A2.06	Fasting serum C-peptide levels out of range	INC3 checked	None
A3	Exclusion criteria violated			
	A3.01	Uncontrolled FPG level	EXC1 checked	None
	A3.02	Additional background therapy	EXC2 checked	PPS
	A3.03	Relevant concomitant diagnoses	EXC3, EXC7 checked	None
	A3.04	Bariatric or other relevant gastrointestinal surgery within the past two years	EXC6 checked.	PPS
	A3.05	Blood dyscrasias or any disorders causing hemolysis or unstable red blood cell	EXC8 checked	PPS
	A3.06	Indication of liver disease	EXC4 checkedParameters above 3 ULN at screening or during run-in period	None
	A3.07	Contraindication to any of the drugs in the study regimen	EXC9 checked	None
	A3.08	Treatment with protocol excluded anti-obesity drugs	EXC11 checked	PPS
	A3.09	Renal insufficiency or renal impairment (assessed by eGFR)	EXC5 checked: eGFR < 45mL/min/1.73m  during screening or run-in period	PPS
	A3.10	Treatment with protocol excluded systemic steroids or change in thyroid hormone dose	EXC12 checked	PPS
	A3.11	Intake of an investigational drug in another trial within 30 days prior to intake of study medication in this trial	EXC15 checked, review at MQRM/BRPM to determine efficacy impact (Medical judgement), depending on the type of drug given in the prior trial (only if investigational drug interferes with glucose metabolism).	PPS Final decision at the DBL meeting
	A3.12	Specific exclusion criterion for pre-menopausal women violated	EXC13 checked	None

Proprietary confidential information © 2017 Boehringer Ingelheim International GmbH or one or more of its affiliated companies

Category / Code	Description	Comment/Example	Excluded from
	A3.13	Relevant alcohol or drug abuse and other conditions affecting study compliance	EXC14 checked  None
	A3.14	Any other clinical condition unsafe for participation that would jeopardize patient safety while participating in this clinical trial	EXC16 checked.  None
	A3.26	Known allergy or hypersensitivity to insulin or empagliflozin	EXC10 checked  None
B	Informed Consent		
	B1	Informed consent not available  INC8 checked, No signature, or Inform consent date missing Patient's data will not be used at all	All
	B2	Informed consent too late  INC8 checked Inform consent date > Visit 1 date/date of any study procedure	None
C	Trial medication and randomisation		
C1	Incorrect Trial Medication Taken		
	C1.01	No study medication taken  Patient randomised according to IRT but no medication taken according to eCRF or IRT	TS
	C1.02	Incorrect trial medication taken  Wrong medication taken for more than 20% of the treatment duration up to Visit 10 or for more than 20% of the last visit interval before the primary endpoint assessment (different medication than the patient was randomised to taken i.e. drug kit recorded in eCRF from different treatment group than drug kit assigned by IRT) Can only be judged after DBL since unblinding information is required	PPS
C2	Randomisation not followed		
	C2.01	Treated without randomisation  Patient treated according to eCRF but not randomised according to IRT.	PPS
C3	Non-compliance		
	C3.01	Non-compliance with drug intake  During the treatment period, overall study treatment compliance up to Visit 10 outside 80% and 120% (exclusive) or study treatment compliance below 80% in the last visit interval up to Visit 10.	PPS
	C3.03	Last treatment more than 7 days prior to next visit  Last treatment prior to Visit 10 was more than 7 days prior to next visit.	PPS

Category / Code	Description	Comment/Example	Excluded from
C4.01	Medication code broken without just cause	Medication code was broken prior to Visit 10 for no valid reason. [manual check. Final decision at the DBL meeting based on medical judgement. This decision will overwrite the programmed result.]	PPS Final decision at the DBL meeting
	Concomitant Medication		
D2	Prohibited medication use		
D2.01	Use of prohibited medication	Review of eCRF for prohibited medication. If first prohibited medication was taken prior to Visit 10 then exclude from PPS. If first prohibited medication was taken between Visit 10 and end of treatment then do not exclude from PPS. [manual check. Final decision at the DBL meeting based on medical judgement. This decision will overwrite the programmed result.]	PPS/None
D3	Mandatory medication not taken		
D3.01	Background antidiabetic therapy not taken as specified in the protocol	- Changes in insulin total daily dose outside +/-10% or +/-2U range from baseline prescribed dose before Visit 10 for more than 7 consecutive days and not for rescue (exclude from PPS). If the change in insulin consists of several records of consecutive changes, it will be considered "not for rescue" only if none of the records are checked at "Yes" for "Rescue medication" in eCRF.	PPS
E	Missing data		
E1.01	No baseline HbA1c value	No valid baseline HbA1c value	FAS
I2	Pregnancy monitoring		
I2.01	Pregnancy	Positive pregnancy test or manual iPV	None
I2.02	Pregnancy test not done for woman of child bearing potential for at least one visit before treatment discontinuation		None

### **6.3 PATIENT SETS ANALYSED**

The following analysis sets will be defined for this trial.

- **SCR – Screened patients set**  
All patients screened for the trial, with informed consent given and who completed at least one screening procedure at Visit 1.

- RS – Randomised set  
All patients from the screened set who were randomised to study drug, regardless of whether any study drug was taken.
- TS – Treated set  
All patients randomised and treated with at least one dose of study drug. The TS is the basis for safety analyses.
- FAS – Full analysis set  
All patients randomised, treated with at least one dose of study drug, and with a baseline HbA1c value. The FAS is the basis for the ITT analysis.
- PPS – Per-protocol set  
All patients in the FAS without IPV leading to exclusion. See [Table 6.2:1](#).

In [Table 6.3: 1](#) the data sets which are to be used for each category class of endpoint are illustrated.

Table 6.3: 1 Summary of which data sets will be used for which class of endpoints

#OR results will only be presented for time to first rescue medication and number of patients with rescue.

^ OC-IR will only be used for lipids.

Similarly, note that patient set PPS is only applicable to analysis performed at week 16.

Note that the number of patients with available data for an endpoint may differ. For details, see [Section 6.6 “Handling of missing data”](#).

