### Observed cases analysis at week 16 (OC-16)

For efficacy endpoints at week 16, it is planned to analyse only the available data that were observed while patients were on treatment, i.e., excluding the missing data. In other words, OC-16 analysis will be performed and missing data in this analysis will not be replaced.

This OC-16 technique will set all values measured after rescue medication taken to missing.

The criterion for rescue medication for this analysis types is based on the definition of rescue medication for the analysis of efficacy endpoints at week 16, as described in [Section 5.3.3.1](#). It includes changes in insulin above and/or below the range +/- 10% or +/- 2U from the baseline prescribed dose for 8 consecutive days or more.

As insulin dose can be adjusted after Visit 10, values collected after visit 10 will also be set to missing for the OC-16 technique.

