### Last observation carried forward (LOCF-16, LOCF-52 and LOCF-IR)

An alternative method for quantitative endpoints is to replace missing values due to early discontinuation of a patient by her/his last observed measurement. This method tends to result in more conservative estimates than an OC-analysis.

The last observation need not necessarily be a value selected as a visit value if multiple measurements were performed within a time window for a visit. In this case the last on-treatment value within the time window will be carried forward, while the visit value can be the value that was observed closest to the planned visit date or the first value observed in the time window. See [Table 6.7: 2](#) for further details.

If a patient is on rescue medication after Visit 5 and before Visit 6, then all the on-treatment visits will be set to missing and the baseline HbA1c value will be carried forward to populate the missing on-treatment values in HbA1c.

Missing values within a course of measurements will be interpolated based on the last observed value before the missing visit and the first observed value after the missing visit. This is independent from the selection of a value as the picked visit value to be used in the descriptive analysis by visit.

Let:

$D_0$  = date of a visit with a missing endpoint value;

$D_1$  = date of the next-visit (with end-point value non-missing) after the visit with missing endpoint;

$D_{-1}$  = date of a previous-visit (with end-point value non-missing) before the visit with missing endpoint;

$E_i$  = endpoint values for visits  $D_{-1}, D_0, D_1$  for  $i = -1, 0$  and  $1$ .

Then the missing endpoint value can be interpolated as:

$$E_0 = E_{-1} + ((E_1 - E_{-1}) \times (D_0 - D_{-1}) / (D_1 - D_{-1})).$$

In general, the values measured after rescue medication was taken during the active treatment period by the patients will be set to missing; and these missing values will be imputed by LOCF technique.

As for the OC techniques, two approaches will be used for the criteria of rescue medication, whether we are analysing efficacy endpoints at week 16 or at week 52 (see [Section 5.3.3.1](#) for more details):

- LOCF-16 will be based on the definition of rescue medication for the analysis of efficacy endpoints at week 16
- LOCF-52 will be based on the definition of rescue medication for the analysis of efficacy endpoints at week 52

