For the LOCF-16 technique, as insulin dose can be adjusted after Visit 10, values collected after visit 10 will also be set to missing, and the missing values will be imputed by LOCF.

Another technique, LOCF including values on rescue medication (LOCF-IR), will be used, when values measured after initiation of rescue medication are not set to missing. For analyses at week 16, the values after the visit 10 date will be set to missing prior to LOCF-IR imputation.

Missing data will only be imputed up to the planned visit to be reached by all randomised patients (week 16 for LOCF-16, week 52 for LOCF-52).

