### **7.8.6 Lipid parameter and FFA analyses**

Lipid parameters and FFA will be analysed using descriptive statistics and MMRM modelling. Descriptive statistics will be shown over time for the treated set (LOCF-IR and OC-IR) including change from baseline and percent change from baseline. For each lipid parameter and FFA, separate MMRM models will be fitted on the treated set (OC-IR) for both change from baseline at week 52 and percentage change from baseline at week 52 as dependent variables. The MMRM models will include ‘baseline lipid’ (only for lipid parameters), ‘baseline FFA’ (only for FFA) and ‘baseline HbA1c’ as continuous covariates and ‘baseline eGFR (Japanese formula)’, ‘type of insulin therapies’, ‘treatment’, ‘visit’ and ‘treatment by visit interaction’ as fixed effects.

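### Does the plan fail to test how the week-16 HbA1c result depends on removing values after an insulin change?

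*SAP*

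**What the plan says.** SAP 7.4 sets the primary analysis as the FAS with LOCF-16. SAP 6.6 gives the general LOCF rule: "In general, the values measured after rescue medication was taken during the active treatment period by the patients will be set to missing", after which LOCF fills the gap. A special case covers very early rescue: "If a patient is on rescue medication after Visit 5 and before Visit 6, then all the on-treatment visits will be set to missing". HbA1c for such a patient is filled from the baseline measurement.

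The observed-case counterpart does the same: "This OC-16 technique will set all values measured after rescue medication taken to missing". For week-16 endpoints, rescue includes "changes in insulin above and/or below the range +/- 10% or +/- 2U from the baseline prescribed dose for 8 consecutive days or more".

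Protocol 7.3.1 names two sensitivity analyses, the same ANCOVA on the PPS with LOCF and an observed-case MMRM on the FAS. It adds that further ones may be performed and will be specified in the SAP. Protocol 7.5 says that censored efficacy data become missing and that different missing-data methods are then applied.

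SAP 6.6 also defines techniques that keep values after rescue. For OC-IR, the footnote to Table 6.3: 1 reads "OC-IR will only be used for lipids". For LOCF-IR, the text is "LOCF including values on rescue medication (LOCF-IR), will be used, when values measured after initiation of rescue medication are not set to missing", with its own cut-off: "For analyses at week 16, the values after the visit 10 date will be set to missing prior to LOCF-IR imputation". The visible application is in SAP 7.8.6: "Descriptive statistics will be shown over time for the treated set (LOCF-IR and OC-IR"), for lipids and FFA.

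**The concern.** Read quickly, the three named week-16 analyses share one step. Each appears to discard HbA1c after a lasting out-of-range insulin change before anything else is done. Agreement among them would then reflect the analysis set and the missing-data method, and would say nothing about the discarding itself.

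The discarded values should largely exist, because Protocol 4.2.1 keeps rescued patients on study drug and in the trial. The removal could also differ by arm. Protocol 2.3 expects more treatment failure on placebo, and says that hypoglycaemia may be more frequent with empagliflozin plus insulin than with insulin alone. With OC-IR confined to lipids, a reader may conclude that the plan holds the right tool but keeps it from the primary endpoint. At stake would be the size of the HbA1c effect, and whether three concordant results were mistaken for support of an untested rule.

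**Working it through.** **1. Which techniques keep values after an insulin change**

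| Technique | Values after an out-of-range insulin change | Scope in visible text |
|---|---|---|
| LOCF-16, OC-16 | set to missing | week-16 efficacy endpoints |
| OC-IR | kept | lipids (footnote); SAP 7.8.6 also uses it for FFA |
| LOCF-IR | kept | no endpoint restriction in 6.6; visible use in 7.8.6 |
| OC-52, LOCF-52 | kept; insulin changes are not rescue, and for OC-52 Visits 5-10 are named explicitly | week-52 endpoints |

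The footnote restricts OC-IR only. LOCF-IR sits under a method introduced for quantitative endpoints and has a week-16 cut-off. The visible lipid and FFA models in 7.8.6 are for week 52. This does not prove that LOCF-IR is used for HbA1c, but nothing visible rules it out.

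**2. What cannot be seen**

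The body of Table 6.3: 1, which assigns techniques to endpoints, is not shown. Nor is Section 5.3.3.1, which defines rescue. In the SAP contents, three untitled entries (pages 29, 30 and 30) stand between 7.4.1 (page 28) and 7.7 (page 31). Section 7.5, visible in the body, and the unseen 7.6 would fill two of them if each has one entry. That leaves one directly after the primary analysis, the natural place for the sensitivity analyses that Protocol 7.3.1 defers to the SAP. This is inference, but it shows that absence cannot be asserted.

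**3. Do the three named analyses differ only in the missing-data step?**

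No. The PPS analysis also changes the population. Violation D3.01 in SAP Table 6.2: 1 excludes patients whose insulin was out of range for more than 7 consecutive days before Visit 10 and not for rescue. The PPS drops these patients, whereas the FAS rule replaces their later values. It does not restore those values, but it handles some of the same patients differently.

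**4. Size**

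Inputs from Protocol 7.7: difference 0.5, SD 1.0, 86 analysed per arm, 90% power, two-sided 5%.

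Plan's own figure: the normal approximation gives 2 x (1.960 + 1.282)^2 x 1.0^2 / 0.5^2 = 84.1, so 85. The t-test has power 0.8999 at 85 and 0.9032 at 86, so 86 is reproduced. Allowing 3% loss, 86 / 0.97 = 88.7, so 89 per arm and 3 x 89 = 267.

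Standard error of a difference: 1.0 x sqrt(2/86) = 0.1525.

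LOCF fills every FAS patient under both rules. With the effect taken as placebo minus empagliflozin, the LOCF-16 effect minus the LOCF-IR effect is

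gap = pP x dP - pE x dE,

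where p is the share of the placebo (P) or empagliflozin (E) arm whose week-16 value is replaced, and d is the mean of replaced minus observed value. The documents give neither p nor d, so all values below are assumptions.

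- 8 placebo (d = +0.5) and 5 empagliflozin (d = -0.3), a post-baseline value carried forward: 8/86 x 0.5 + 5/86 x 0.3 = +0.064.
- Same counts, baseline carried forward (d = -0.3 and +0.4): -8/86 x 0.3 - 5/86 x 0.4 = -0.051.
- 2 and 2 patients: +0.019 and -0.016.
- 13 and 9 patients: +0.107 and -0.087.

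All are below 0.1525, and the sign depends on which value is carried forward.

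Thresholds, as a net number out of 86:

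- One standard error: 0.1525 x 86 / d = 13.1 at d = 1.0 (14 patients) or 26.2 at d = 0.5 (27).
- Edge of significance from an effect of 0.5: 0.5 - 1.96 x 0.1525 = 0.201. This needs 0.201 x 86 / d = 17.3 (18 patients) or 34.6 (35).

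A harsher illustration takes the difference with all values kept as 0.5 minus (placebo excess of insulin changes) x (HbA1c effect of the change):

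| Placebo excess | Insulin effect 0.5 | Insulin effect 1.0 |
|---|---|---|
| 5 points | 0.475 | 0.45 |
| 10 points | 0.45 | 0.40 |
| 20 points | 0.40 | 0.30 |

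Only the last cell moves the effect by more than one standard error (0.20 against 0.1525). It assumes about 17 more placebo patients out of 86 with a lasting change, each worth a full 1.0 HbA1c point.

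**The case for a change.** The strongest reply is that no visible HbA1c analysis at week 16 keeps the removed values, and that SAP Section 4 says everything in it was already outlined in the protocol, which names only two sensitivity analyses. A confirmatory line and one rerun of an existing model would cost little, and the values are collected anyway.

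Part of this stands. If the sensitivity analyses use the week-16 rules, as SAP 6.6 implies, their agreement does not test the removal rule, and a report should not present it as if it did. But Section 4 does not close the matter, because the protocol itself provides for further sensitivity analyses specified in the SAP.

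The request is also for a different estimand. Protocol 2.2 sets the week-16 question as add-on to stable insulin, and removing values once insulin has lastingly left the allowed range serves that question. Insulin as actually adjusted belongs to the second, adjustable-dose objective, and OC-52 and LOCF-52 retain values after insulin changes for it. Protocol 7.5 promises to vary the missing-data methods, not the censoring rule, so no promise is broken. Numbers of patients with rescue and time to first rescue are already planned in the notes to Table 6.3: 1.

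**Conclusion.** No defect is shown. The narrow observation is fair: LOCF-16 and OC-16 both remove HbA1c after a lasting out-of-range insulin change. The step from there to a gap in the plan relies on text that is blacked out, while the visible text leaves LOCF-IR open for week-16 HbA1c. The primary analysis is not in error, and the removal is consistent with the stable-insulin objective.

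On assumed counts of 2 to 13 patients per arm, the gap runs from -0.09 to +0.11 against a standard error of 0.152. Bringing an effect of 0.5 to the edge of significance would take a net 18 to 35 of 86 patients, at d of 1.0 and 0.5 respectively. These figures rest on assumed rates and shifts, because the documents give none, and on the planning values in Protocol 7.7. They do not prove that the influence is negligible. The conclusion rests mainly on the reading of the rules.
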